3.1.1.1 Safety of Pfs25H-EPA/Alhydrogel® in Healthy US Adults

[figure not shown]
Vaccinations were well-tolerated, with minimal local and systemic reactogenicity.^{15,23} There was an increase in the percentage of subjects reporting solicited adverse events (AEs) with each escalating dose, with AEs diminishing with each subsequent dose of vaccine given. No subjects were withdrawn due to related adverse events. A single serious adverse event (SAE) occurred during the course of the study that was unrelated to the vaccine. These findings are summarized in [Figure 4](#).

Figure 4: Related Local Injection Site Reactogenicity and Systemic Adverse Events.

All injection site reactogenicity was deemed related to Pfs25H-EPA/Alhydrogel®. Clinical solicited (A-C) adverse events after each vaccination with each dose group are reported in individual graphs: Group 1a (A), 1b (B) and Group 2 (C). All adverse events were mild except when indicated as moderate.

[figure not shown]
All laboratory adverse events (related and unrelated) are shown in [Figure 5](#). While several subjects experienced anemia after vaccination, the majority of these events were judged to be unrelated to vaccination, either because these subjects had low, but normal, hemoglobin levels at baseline (day of first vaccination) or because of an alternate explanation (e.g., blood donation or previously undisclosed history of anemia). An examination of trends in hematologic parameters does not show any pattern related to timing of vaccinations.¹⁵

Figure 5: Laboratory Adverse Events

Laboratory (A-C) adverse events after each vaccination with each dose group are reported in individual graphs: Group 1a (A), 1b (B) and Group 2 (C). All adverse events were mild except when indicated as moderate. All neutropenia events occurred in the same subject. All hematuria occurred during menses. All leukopenia events occurred in the same subject. All laboratory adverse events except for a portion of the decreased hemoglobin (n=10) were found by the PI to be unrelated to Pfs25H-EPA/Alhydrogel[®]

[figure not shown]

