Each field has the format # (X) %, where # is the number of adverse events, X is the number of subjects with one or more episodes of the given event, and % is the number of participants with one or more episodes of the given event divided by the total number of participants who received the study agent (N) multiplied by 100.

Safety analysis of the high dose of Pfs25M-EPA/Alhydrogel[®], 47µg of Pfs25M (Arm A2), is in process following unblinding in April 2017. Overall, in the blinded cohort, the majority of reported AEs have been mild (Grade 1; 708/1431; 49%) with the most commonly report AEs being injection site pain, headache, malaria, neutropenia, nasopharyngitis, and rhinitis. The most commonly reported related AEs have been injection site reactogenicity (pain, induration, pruritus, and edema), leukopenia, neutropenia, and headache, which have been all Grade 1 or 2.

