12.3 Investigator Assessment of Adverse Events

If a diagnosis is clinically evident (or subsequently determined), the diagnosis rather than the individual signs and symptoms or lab abnormalities will be recorded as the AE.

All solicited (see [Table 14](#) below) and unsolicited AEs will be recorded through Day 7 after each vaccination, including injection site reactions, or until resolved. Adverse reactions related to direct skin feeds will be recorded until Day 7 after feeds or until resolved. After that period only unsolicited AEs (including symptomatic malaria), SAEs, UPs, and NOCIs will be recorded. Note that a positive blood smear without associated clinical symptoms will not be reported as an AE.

Table 14: Solicited Adverse Events

Systemic adverse events
Fever (temperature ≥ 38.0 °C)
Headache
Nausea/Vomiting
Diarrhea
Abdominal pain
Fatigue
Myalgia
Arthralgia
Urticaria
Laboratory adverse events
Hemoglobin – decreased hemoglobin
WBC – leukopenia, leukocytosis
ANC/AGC – decreased neutrophil/granulocyte count

Platelet count – thrombocytopenia
ALT – increased ALT
Creatinine (Cr) – increased Cr
Local reactogenicity
Injection pain/tenderness
Injection erythema/redness
Injection swelling
Injection induration
Injection pruritus
Limitation of arm movement

Additional laboratory abnormalities other than those specified as safety labs in the protocol should be reported as adverse events if they require intervention. Interventions include, but are not limited to, discontinuation of treatment, dose reduction/delay, additional assessments, or concomitant treatment. In addition, any medically important laboratory abnormality may be reported as an adverse event at the discretion of the investigator. This could include a laboratory result for which there is no intervention but the abnormal value suggests a disease or organ toxicity. In addition, similar to solicited AEs, all laboratory AEs as defined in [Appendix D](#), will be collected and graded through 7 days after each vaccination or until resolved.

The investigator will evaluate all AEs with respect to Seriousness (criteria listed above), Severity (intensity or grade), and Causality (relationship to study agent and relationship to research) according to the following guidelines.

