14.2 Primary Objective

The primary objective of this study is to assess safety and reactogenicity of Pfs25M-EPA/AS01 and Pfs230D1M-EPA/AS01 in Malian adults.

- The frequency of systemic and local AEs will be summarized.
- A line listing of each clinical and laboratory AE classified as local, solicited, or other will be displayed in tables stratified by vaccine allocation.
- AEs will be summarized by severity and relationship to vaccine
- The proportion of subjects with at least 1 AE will be compared by vaccine schedule and/or dose group, and tests will be performed to assess whether these groups differ with respect to these proportions. To evaluate the difference in AEs between the initial vaccination and the subsequent vaccinations, a Wilcoxon signed rank test will be performed, where the response for each subject is the difference between the numbers of AEs in the 7 days following each vaccination. To compare number and severity of AEs between control and vaccine arms, Wilcoxon-Mann-Whitney test (also known as Wilcoxon rank sum test and the Mann-Whitney U test) tests as well as linear regression may be used.
- SAEs occurring within the study period will be listed by relationship to vaccine.

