14.5 Sample Size and Power Calculations

SAFETY

The arms of five subjects are sized for safety, as the higher dose is expected to be necessary for an adequate immune response. In these arms (Arms 1a, 2a, 3a), 5 subjects each will receive 16 μg of Pfs25M-EPA/AS01 or 13 μg Pfs230D1M-EPA/AS01 or the combination of both.

Vaccination arms of 5 subjects gives a probability of at least 0.80 for detecting 1 or more serious or severe AEs that occur with a probability of 0.275 or more per subject.

For each dose level that has a ($n=10$) in Arms 1b, 2b, 3b, vaccination of 10 subjects gives a probability of at least 0.90 for detecting 1 or more serious or severe AEs that occur with a probability of 0.206 or more per subject.

For each dose level that has a (n=60) in Arms 2c, 2d, and 4c, vaccination of 60 subjects gives a probability of at least 0.90 for detecting 1 or more serious or severe AEs that occur with a probability of 0.038 or more per subject.

If we combine all treated groups in Mali (Arms 1a, 1b, 2a, 2b, 3a, 3b, 2c and 2d), 165 subjects, we have 95% power to detect 1 or more serious or severe AEs that occur with a probability of 0.018 or more per subject. Due to arms having varying doses, combinations and administration villages, this analysis would only be done to catch an AE that transcended these discrepancies.

We will compare all AE event proportions between the control arm and treated arm by Fisher's exact test.

ELISA ANALYSIS

There are several questions of interest based on the antibody response information after the 2nd, 3rd and for arms 2c, 2d, and 4c, a 4th (booster) doses of the respective vaccines. We are interested in the change in ELISA values from baseline to after a given number of doses of vaccine, and the change in ELISA values between doses. For this we will use Wilcoxon signed rank tests (WSRT) within the 60 subjects receiving a given vaccine regimen. We are also interested in the effect of a given number of vaccinations on the ELISA responses as compared to comparator. This comparison can be made by Wilcoxon Mann Whitney (WMW) test, which accommodates the limit of detection issues that may exist for ELISA results.

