The following evaluations/procedures will be completed following vaccination:

1. Observe the subject for at least 30 minutes after vaccination to evaluate immediate adverse reactions.
2. Record vital signs (blood pressure, temperature, and heart rate).
3. Perform interim history and physical examination, focusing on any acute complaints.
4. Record AEs and concomitant medications, if applicable.

Study Day 1 (± 0 days; 1 day after Vaccination #1)

1. Perform basic history and focused physical examination (including injection site), emphasizing examination of any acute complaints.
2. Record vital signs (blood pressure, temperature, and heart rate).
3. Record AEs and concomitant medications, if applicable.

Study Day 3 (± 1 day; 3 days after Vaccination #1)

1. Perform basic history and focused physical examination (including injection site), emphasizing examination of any acute complaints.
2. Record vital signs (blood pressure, temperature, and heart rate).
3. Record AEs and concomitant medications, if applicable.
4. Obtain approximately 16 mL of blood for CBC with differential and platelet count, ALT, creatinine, *ex vivo* assays, cellular assays, *ex vivo* assays, and B cell assays, and transcriptional analysis.

Study Day 7 (± 2 days; 7 days after Vaccination #1)

1. Perform basic history and focused physical examination (including injection site), emphasizing examination of any acute complaints.
2. Record vital signs (blood pressure, temperature, and heart rate).
3. Record AEs and concomitant medications, if applicable.

Study Day 14 (± 3 days; 14 days after Vaccination #1)

1. Perform basic history and focused physical examination, emphasizing examination of any acute complaints.
2. Record vital signs (blood pressure, temperature, and heart rate).
3. Record AEs and concomitant medications, if applicable.
4. Obtain approximately 11 mL of blood for CBC with differential and platelet count, ALT, creatinine, malaria blood smear, malaria PCR, and anti-Pfs230 antibody ELISA.

Study Day 28 (day of Vaccination #2)

The following evaluations/procedures will be completed before vaccination:

1. Perform interim history and physical examination, focusing on any acute complaints.
2. Record vital signs (blood pressure, temperature, and heart rate).
3. During the physical examination, study staff will educate the subject regarding signs and symptoms of potential adverse events (AEs) and indications for use of antipyretics if fever, headache, or malaise occurs.

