1. Perform basic history and focused physical examination (including injection site), emphasizing examination of any acute complaints.
2. Record vital signs (blood pressure, temperature, and heart rate).
3. Record AEs and concomitant medications, if applicable.
4. Obtain approximately 16 mL of blood for CBC with differential and platelet count, ALT, creatinine, cellular assays and B cell assays, and transcriptional analysis.

Study Day 483 \pm 2 days (7 days after Vaccination #4)

1. Perform basic history and focused physical examination, emphasizing examination of any acute complaints.
2. Record vital signs (blood pressure, temperature, and heart rate).
3. Record AEs and concomitant medications, if applicable.
4. Obtain approximately 23 mL of blood for cellular assays, *ex vivo* assays, B cells assays, and transcriptional analysis.
5. For females, obtain a urine or serum sample for β -hCG testing. Ensure that the test is negative before completing feed.
6. Feeding evaluations (DSF) will also be performed at this visit.
 - a) Confirm eligible for DSF

Study Day 486 \pm 2 days (10 days after Vaccination #4)

1. Perform basic history and focused physical examination, emphasizing examination of any acute complaints.
2. Record vital signs (blood pressure, temperature, and heart rate).
3. Record AEs and concomitant medications, if applicable.
4. Obtain approximately 2 mL of blood for malaria blood smear and malaria PCR.

5. Feeding evaluations (DSF) will also be performed at this visit.
 - a. Confirm eligible for DSF

Study Day 490 \pm 3 days (14 days after Vaccination #4)

1. Perform basic history and focused physical examination, emphasizing examination of any acute complaints.
2. Record vital signs (blood pressure, temperature, and heart rate).
3. Record AEs and concomitant medications, if applicable.
4. Obtain approximately 17 mL of blood for malaria blood smear, malaria PCR, CBC with differential and platelet count, ALT, creatinine, SMFA, and anti-Pfs230 antibody ELISA and transcriptional analysis.
5. For females, obtain a urine or serum sample for β -hCG testing. Ensure that the test is negative before completing feed.
6. Feeding evaluations (DSF) will also be performed at this visit.
 - a. Confirm eligible for DSF

Study Day 493 \pm 2 days (17 days after Vaccination #4)

1. Perform basic history and focused physical examination, emphasizing examination of any acute complaints.
2. Record vital signs (blood pressure, temperature, and heart rate).

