Hemoglobin (Female) gm/dL	8.0 – 9.0	7.0 – 7.9	6.0 – 6.9	< 6 and /or requiring transfusion
WBC Increase – 10 ³ /μL	11.5 – 15.0	15.1 – 20.0	20.1 – 25.0	> 25.0
WBC Decrease - 10 ³ /μL	2.5 – 3.3	1.5 – 2.4	1.0 – 1.4	< 1.0
Neutrophil/Granulocyte Decrease ³ - 10 ³ /μL	0.80 – 1.00	0.50 – 0.79	< 0.50	< 0.50 with fever
Platelets Decreased – 10 ³ /μL	100 – 115	70 – 99	25 – 69	< 25
Creatinine (Male) μmol/L	132.60 – 159.11	159.12 – 185.63	185.64 – 221.00	> 221.00 and requires dialysis
Creatinine (Female) μmol/L	97.42 – 116.94	116.95 – 136.44	136.45 – 162.43	> 162.43 and requires dialysis
Liver Function Tests – ALT U/L	46.0 – 106.5	106.6 – 209.0	209.1 – 410.0	> 410.0

¹ The laboratory values provided in the table are taken from the FDA Guidance for Industry “Toxicity Grading Scale for Healthy Adults and Adolescent Volunteers Enrolled in Preventive Vaccine Clinical Trials” dated September 2007. The laboratory values provided in the referenced tables serve as guidelines and have been adapted for institutional normal parameters (see below). Institutional normal reference ranges should be provided to demonstrate that they are appropriate.

² The clinical signs or symptoms associated with laboratory abnormalities might result in characterization of the laboratory abnormalities as Potentially Life Threatening (Grade 4). For example, a low sodium value that falls within a grade 3 parameter should be recorded as a grade 4 hyponatremia event if the subject had a new seizure associated with the low sodium value.

³ Note, neutropenias are graded and followed, but based on previous experience in African populations, should be interpreted with caution since lower values are more frequently observed in people of African descent ^{46,47}.

Mali Adult: Institutional Normal Parameters**Chemistry**

Serum¹	Reference Range
Creatinine (Female) - $\mu\text{mol/L}$	< 72
Creatinine (Male) - $\mu\text{mol/L}$	48 – 98
ALT – U/L	< 41

¹The laboratory values provided in the table are based on Bancoumana, Malian adults (age 18-45 years old)

Hematology

Hematology¹	Reference Range
Hemoglobin (Female) - gm/dL	9.1 – 13.8
Hemoglobin (Male) - gm/dL	10.8 – 15.8
WBC – $10^3/\mu\text{L}$	3.6 – 9.0
Absolute Neutrophil/Granulocyte Count - $10^3/\mu\text{L}$	1.3 – 4.4
Absolute Lymphocyte Count - $10^3/\mu\text{L}$	1.3 – 4.4
Platelet Count (Female)- $10^3/\mu\text{L}$	144 – 413
Platelet Count (Male)- $10^3/\mu\text{L}$	114 – 335

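### Laboratory safety data are analysed only as graded adverse events, so a moderate shift in blood counts, ALT or creatinine across a vaccine arm could be missed although the measurements to show it are collected

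*Combined protocol and SAP*

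**What the plan says.** **Measurement.** Appendix C takes safety bloods from the main-study arms at Day -7, before Vaccinations #1, #2 and #3, and 3 and 14 days after each. The Day 3 entry reads "Obtain approximately 16 mL of blood for CBC with differential and platelet count, ALT, creatinine". For Vaccination #4 the pre-dose values come from re-screening, because the Day 476 blood list has no full blood count, ALT or creatinine. Post-dose draws follow on Days 479 and 490; the latter reads "Obtain approximately 17 mL of blood for malaria blood smear, malaria PCR, CBC with differential and platelet count, ALT, creatinine".

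**Analysis.** Section 14.2 provides "A line listing of each clinical and laboratory AE classified as local, solicited, or other will be displayed in tables", summaries by severity and relationship, proportions of subjects with an event, and rank tests or regression on the number and severity of events. Section 14.5 adds: "We will compare all AE event proportions between the control arm and treated arm by Fisher's exact test". Neither section plans a summary of measured values, a change from baseline, a shift table or an arm comparison of laboratory values. Section 9.2 says that the blood-count parameters will be assessed for safety but gives no method.

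**What becomes an event.** Section 12.3 says that laboratory events "will be collected and graded through 7 days after each vaccination or until resolved", so the Day 14 draw falls outside the routine window. Appendix D grades absolute values, for example the row "Neutrophil/Granulocyte Decrease".

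**Background.** Among the commonly reported related events in #15-I-0044, section 3.1.4.1 lists "leukopenia, neutropenia, and headache, which have been all Grade 1 or 2". For the US Pfs25H study, section 3.1.1.1 states: "All laboratory adverse events except for a portion of the decreased hemoglobin (n=10) were found by the PI to be unrelated".

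**The concern.** Safety is the primary objective. A graded event is recorded only when a value crosses a fixed cut-off, whatever the subject's own starting value. If a vaccine lowers counts a little in everyone, only the few subjects already near the cut-off contribute. A neutrophil count that falls from 2.4 to 1.05, or a male haemoglobin that falls from 15 to 10.6 g/dL, reaches no grade. The report could then find no difference in laboratory abnormalities when the collected values would have shown one. Appendix D itself warns that low neutrophil counts are common in this population. That makes each subject's own baseline more informative than an absolute threshold.

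**Working it through.** **1. The plan's own safety figures.** Section 14.5 gives the chance of seeing at least one serious or severe event, 1 - (1 - p)^n:
- n = 5, p = 0.275: 0.800
- n = 10, p = 0.206: 0.900
- n = 60, p = 0.038: 0.902
- n = 165, p = 0.018: 0.950

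All four reproduce. They concern rare severe events and say nothing about shifts in laboratory values, for which the plan gives no power.

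**2. Where Grade 1 starts against the site limit (Appendix D).**

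| Analyte | Site limit | Grade 1 starts |
|---|---|---|
| Neutrophils | 1.3 | 1.00 |
| WBC, low | 3.6 | 3.3 |
| ALT | 41 | 46 |
| Creatinine, male | 98 | 132.60 |
| Creatinine, female | 72 | 97.42 |
| Platelets, female | 144 | 115 |
| Platelets, male | 114 | 115 (inside normal) |
| Haemoglobin, male | 10.8 | 10.5 |
| Haemoglobin, female | 9.1 | 9.0 |

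The gap is real for the first six rows. It is absent for male platelets and slight for haemoglobin, where the loss comes from using a cut-off at all.

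**3. Assumptions for the illustration (none is in the documents).** Pooled vaccine 120 against control 120; one post-dose draw; two-sided 5%; correlation with baseline 0.3 to 0.7; a uniform shift. The base case reads each site range as the central 95% of values.

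- Event analysis: exact power of Fisher's test on the proportions at Grade 1 or worse.
- Value analysis: power = Φ(δ / [σ√(1 - ρ²) × √(2/120)] - 1.96).

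**4. Neutrophils, 10% fall.** Base case: median √(1.3 × 4.4) = 2.39; log-SD = ln(4.4/1.3)/3.92 = 0.311; δ = -ln 0.9 = 0.105. At ρ = 0.5: 0.105 / (0.269 × 0.129) = 3.03, and Φ(3.03 - 1.96) = 0.86.

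The base case puts only about 0.3% of controls at Grade 1 or worse, so backgrounds of 5% and 10% were also tried. They can be reached by widening the spread around the same median or by lowering the median with the same spread.

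| Scenario | Graded, control → vaccine | Fisher | Adjusted (ρ 0.3 / 0.5 / 0.7) |
|---|---|---|---|
| Median 2.39, log-SD 0.311 | 0.3% → 0.7% | <1% | 0.79 / 0.86 / 0.96 |
| Median 2.39, log-SD 0.53 | 5% → 7.4% | 7% | 0.36 / 0.43 / 0.58 |
| Median 2.39, log-SD 0.68 | 10% → 13.0% | 8% | 0.24 / 0.28 / 0.39 |
| Median 1.67, log-SD 0.311 | 5% → 9.6% | 19% | 0.79 / 0.86 / 0.96 |
| Median 1.49, log-SD 0.311 | 10% → 17.3% | 31% | 0.79 / 0.86 / 0.96 |

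Only the first row agrees with reading 1.3-4.4 as the central 95%. The lowered medians put 21% and 33% of subjects below 1.3. The wider spreads put Φ((0.262 - 0.872)/0.53) = 12.5% and Φ((0.262 - 0.872)/0.68) = 18.5% there. The rows therefore bracket what is unknown.

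**5. Haemoglobin, 0.5 g/dL fall, male range.** Mean 13.3; SD = 5.0/3.92 = 1.28. Grade 1 or worse goes from 1.4% to 3.6%, with Fisher power 7%. Adjusted, at ρ = 0.5: 0.5 / (1.105 × 0.129) = 3.51, and Φ(3.51 - 1.96) = 0.94; the range over ρ is 0.89 to 0.99.

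**6. Large falls.** With a 50:50 sex mix, a 1.0 g/dL haemoglobin fall gives Fisher power of 66% (60 against 120) to 72% (120 against 120). With a 10% graded background from a lowered median, a 20% neutrophil fall gives about 95%.

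**The case against.** The strongest reply is that the trial is exploratory, its endpoint is the incidence of adverse events, and section 14.2 matches that endpoint. There are also other safeguards. Section 12.3 lets the investigator report any medically important laboratory abnormality. Halting rule 8 in section 12.9 acts on laboratory grades whatever the attributed cause. The DSMB has received unblinded information throughout. Section 14.2 also allows rank tests and regression on event number and severity, so Fisher's test on a single draw understates what the event analysis can do.

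Part of this stands. Large falls would often be seen, and the power figures are only illustrative. But discretionary reporting works subject by subject and cannot reveal a shift across an arm. Rule 8 and the rank tests still depend on grades. Section 14.1 promises estimates with 95% confidence intervals, and that is what is missing for the measured values.

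A reader might go further and infer that the predecessor trials showed a laboratory signal for these conjugates. The documents do not support that:
- The related leukopenia and neutropenia in #15-I-0044 come from a blinded cohort pooled with its comparator.
- In the US Pfs25H study most anaemia events were judged unrelated, and a check of haematology trends found no pattern with vaccination.
- The Malian Pfs25H study found no difference from comparator in laboratory abnormalities.

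Nor are laboratory values the only objective safety measures. Vital signs are graded numerically, and the diameter of local reactions is recorded as a continuous variable.

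**Conclusion.** The point holds for moderate shifts. The plan turns repeated laboratory measurements into graded events and specifies no analysis of the values. In every scenario tried, the baseline-adjusted comparison had more power than Fisher's test. For a 10% neutrophil fall it was 79-96% or 24-58%, depending on the spread, against below 1% to 31%. For a 0.5 g/dL haemoglobin fall it was 89-99% against 7%. The size rests on the assumed spread, correlation, uniform shift and single draw. With a wide spread the adjusted analysis is better but far from certain to detect a 10% fall.

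Two stronger readings should be avoided. It is not true that every cut-off lies beyond the site's limits: male platelets do not fit, and haemoglobin barely does. Nor would any fall go unnoticed, since large ones would often appear as graded events or under halting rule 8. The safety sizing in 14.5 is correct and unaffected. This is a gap in the analysis plan, not evidence of harm.

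**What to change.** Keep the graded event tables and add to section 14.2, for haemoglobin, WBC, neutrophils, platelets, ALT and creatinine in the randomised main-study arms:

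- The vaccine-minus-control difference at Days 3 and 14 after each dose, with a 95% confidence interval. Use a linear model (log scale where skewed) adjusted for the pre-Vaccination #1 baseline, sex and village. State in advance how the Day -7 and Day 0 values form that baseline.
- Change from the most recent pre-dose value as a descriptive display only. From Vaccination #2 on, that value is itself post-vaccination, and adjusting for it could remove a sustained or cumulative fall.
- A shift table from baseline to worst post-dose category, with a category for values outside the site's normal range but ungraded.
- A note that Vaccination #4 is open-label and that its pre-dose laboratory values come from re-screening.

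No grading cut-off, halting rule or clinical rule changes, and no new samples are needed. The cost is protocol or SAP wording and a few extra tables. Six analytes at several time points will produce some chance differences, so the results should be reported as estimates with intervals rather than as tests.

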3.5.2 Evaluation of Fourth Vaccination (Main/Bancoumana-Doneguebougou)

3.5.2.1 Safety

In the blinded Activity Main Phase, most AEs reported have been mild or moderate with most AEs being unrelated to vaccination (1830/2336, 78%). Of the related AEs (506/2336, 22%), the majority have been mild (Grade 1; 423/506, 84%), with the most commonly reported related AEs being local site reactogenicity (369/506, 73%; Grade 1: 324/369, 88%; Grade 2: 45/369, 12%) and mild (Grade 1) solicited systemic reactogenicity (e.g. headaches, fever, myalgias, arthralgias). Local injection site pain did not appear to increase in severity or frequency with subsequent vaccinations, but following Vaccination #2 the occurrence of other local site reactogenicity (edema, pruritus, impairment of movement, redness) appeared to be reported more frequently, but not post Vaccination #3.

Various laboratory abnormalities have been noted, though most of them have been mild (Grade 1) and transient. A few Grade 2 (moderate) neutropenias and leukopenias have been reported. But no laboratory abnormalities have been reported in the frequency or intensity meeting further evaluation or study halt. As expected, given the time of year, the number of malaria cases has increased overall post Vaccination #3.

A total of thirty-seven Grade 3 AEs have been reported (malaria, snake bite, pyrexia, bronchitis, systolic hypertension), all determined as not related to vaccination. A single SAE (snake bite) was previously reported and has resolved completely.

In summary, vaccinations have been well tolerated with no identified safety concerns at this time, but safety will be further assessed upon scheduled, intentional unblinding.

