14.1 Description of Statistical Methods

This study, like other Phase 1 studies, is exploratory rather than confirmatory; its purpose is to estimate AE rates and patterns of immune responses rather than to test formal statistical hypotheses. Estimates will be presented with their 95% confidence intervals. Descriptive approaches will be used to meet the protocol objectives, as well as formal statistical tests as outlined below. Results will be presented in tabular format, as well as graphically where appropriate.

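### In the main phase, the committed test of subjects with any AE sits near its ceiling, and the dose 1 v dose 3 signed-rank comparison has no control adjustment for malaria season

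*Combined protocol and SAP*

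**What the plan says.** Section 14.2 plans the following for the primary objective.

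- A test of proportions: "The proportion of subjects with at least 1 AE will be compared by vaccine schedule and/or dose group". No AE category or time window is attached.
- A within-subject Wilcoxon signed-rank test of the initial v subsequent vaccinations, "where the response for each subject is the difference between the numbers of AEs in the 7 days following each vaccination".
- An arm comparison: "To compare number and severity of AEs between control and vaccine arms, Wilcoxon-Mann-Whitney test" and linear regression. Both are only methods that may be used, and neither is limited to solicited or related AEs.
- A descriptive part: "AEs will be summarized by severity and relationship to vaccine".

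Section 14.5 adds "We will compare all AE event proportions between the control arm and treated arm" by Fisher's exact test, again without naming categories. Section 14.1 describes the study as "exploratory rather than confirmatory; its purpose is to estimate AE rates" and patterns of immune response, but it also promises formal tests.

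Two rules elsewhere decide what counts as an AE. Section 12.3 continues to record unsolicited AEs, including symptomatic malaria, after Day 7. Section 12.3.2 classes every malaria case as unrelated but still reports clinical malaria as an AE.

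**The concern.** Read as written, the any-AE proportion is all-cause and covers the whole study. In a malaria-endemic village followed for most of a year, nearly everyone will have had some illness, so vaccine and control arms meet at the top of the scale. A null result would then say little about the vaccine, yet it could be quoted as reassurance on the primary objective.

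The signed-rank test has a different problem. Accrual ran from about December to April (Protocol Summary), and transmission at Doneguebougou runs from June to December (section 6.2.1.2). Doses 1 and 2 therefore fall mostly before the season, and dose 3 on Day 168 falls inside it. Section 3.5.2.1 confirms that malaria increased after dose 3. In Arm 2d the third dose is also one fifth of the full dose. A within-arm change from dose 1 to dose 3 mixes these effects with any true change in reactogenicity, and the plan names no comparison of that change with Arm 4c.

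**Working it through.** **The plan's own figures.** Section 14.5 gives only the probability of seeing at least one serious or severe AE, 1 − (1 − p)^n. For n = 5, 10, 60 and 165 with p = 0.275, 0.206, 0.038 and 0.018, this gives 0.80, 0.90, 0.90 and 0.95. All four reproduce. No power is given for the any-AE test or the signed-rank test.

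**How close to the ceiling?**
- Predecessor trial #13-I-N109, Table 2B: any AE in 50/50 vaccinees v 49/50 controls; Fisher p = 1.00.
- This trial's main phase, section 3.5.2.1: 2336 AEs, of which 1830 unrelated. With 240 planned subjects, 2336/240 = 9.7 per subject and 1830/240 = 7.6 unrelated.
- Implied P(at least one AE) at a mean of 9.7: 99.99% if Poisson; 97% or 91% if negative binomial with k = 2 or 1.

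**Power of the any-AE test.** Exact Fisher enumeration, 60 v 120. Two-sided alpha of 0.05 is assumed, since that level is stated only for the ELISA test.
- If all 60 vaccinees have an AE, 8 AE-free controls of 120 give p = 0.053 and 9 give p = 0.030. At least 9 (7.5%) are therefore needed.
- 100% v 98%: 0.07% (3% with the two vaccine arms pooled, 120 v 120).
- 100% v 95%: 15%. 100% v 90%: 86%.

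**Vaccine-attributable endpoints in the predecessor.** Section 3.1.2.1 reports no difference in number of AEs, but differences in solicited (p = 0.01) and related (p = 0.019) AEs. These two p-values cannot be re-derived, because Table 2 gives no subject counts for those categories. Using Table 2B's cumulative four-dose rates at 60 v 120:

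| Endpoint | Vaccine v control | Power |
|---|---|---|
| Local reactogenicity | 78% v 62% | 58% |
| Systemic reactogenicity | 40% v 24% | 55% |
| Related Grade 2 | 40% v 10% | 99% |

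Per dose, related Grade 2 was 12 v 4%, 14 v 4%, 11 v 5% and 24 v 5%. Power is then 47%, 61%, 28% and 94%.

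**What the 7-day window contains.** Assume all 506 related AEs fell inside the windows of three doses: 506/(240 × 3) = 0.70 per dose. Unrelated AEs spread evenly over an assumed 48 weeks give 7.6/48 = 0.16 per 7 days. The related share is 0.70/(0.70 + 0.16) = 82%. If all unrelated AEs fell within 24 weeks, the rate is 0.32 and the share 69%. Over the whole study it is 506/2336 = 22%.

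**Season bias in dose 1 v dose 3.** Poisson simulation, 2000 runs, with related AEs held constant and only the unrelated 7-day rate changing (assumed rates):

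| Unrelated rate, dose 1 to dose 3 | Rejection, n = 60 | Rejection, n = 120 controls |
|---|---|---|
| 0.15 to 0.15 | about 5% | about 6% |
| 0.10 to 0.27 | 14–19% | 35% |
| 0.05 to 0.32 | 28–43% | 72% |

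For comparison, a real fall in related AEs from 0.9 to 0.5 per dose with no season effect is detected 64% of the time at n = 60.

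**The optional arm comparison.** With an assumed 0.9 v 0.5 related AEs per dose over three doses, WMW power is 65% on whole-study all-cause counts and over 99% on counts within the 7-day windows. With 0.84 v 0.56 it is 39% and 90%.

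**The case against.** The strongest reply is that the plan has more than these two tests. The WMW or regression comparison and the Fisher tests of section 14.5 can show a vaccine effect, relatedness is summarised, the primary endpoint is the incidence of local and systemic AEs and SAEs, and the study is declared exploratory. This stands in part. A reader might infer that the primary safety analysis cannot show a vaccine effect at all; the documents do not support that. But the WMW comparison is optional and not limited to solicited or related AEs, the Fisher tests name no category, and the relatedness summary involves no test.

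Four other stronger readings are also tempting and should be resisted.

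- That the signed-rank test measures malaria season. It is confined to 7 days after each dose, where most AEs are probably vaccine-related. Doses 1 and 2 are 28 days apart, so that comparison is little affected. It was also never the vaccine v control test.
- That Table 2B shows a large seasonal rise because unsolicited AEs in controls went from 67 in 50 subjects after dose 1 to 250 in 42 after dose 3. The predecessor dosed at 0, 2, 4 and 16 months, so the intervals are 2 and 12 months: 67/50/2 = 0.67 v 250/42/12 = 0.50 per subject-month, which is no rise.
- That the proportion is saturated in every arm. Pilot Arm 1b had 30 AEs in 10 subjects, and Arms 4a/4b had 67 in 20. This implies 95–96% with at least one AE if Poisson, but only 75–86% if overdispersed.
- That the 99% power carries over to single doses. It rests on a rate accumulated over four doses.

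**Conclusion.** The point holds for Arms 2c, 2d and 4c. The any-AE proportion is close to uninformative: power is 0.07% at the predecessor's rates and 15% even if controls were at 95%. The dose 1 v dose 3 signed-rank comparison is biased, not dominated, by season; the size of the bias depends on 7-day rates that the documents do not report. Because the study is exploratory, this is an uninformative test rather than a failed confirmatory one. It still deserves correction, since the predecessor's own results show where a difference can be seen.

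The conclusion rests on an assumed alpha of 0.05, 240 subjects as denominator, pooled blinded AE counts, and Alhydrogel-adjuvanted Pfs25H rates as planning values for an AS01-adjuvanted Pfs230D1M vaccine. Table 2B's rates are also not confined to 7 days.

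**What to change.** For the main phase, replace the any-AE test with the proportions of subjects having, within 7 days of any of doses 1 to 3, at least one solicited local AE, at least one solicited systemic AE, and at least one related Grade 2 or higher AE. Compare each of Arms 2c and 2d with Arm 4c. Report per-dose results and all-cause AEs descriptively with 95% confidence intervals.

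Limit the signed-rank test to solicited AEs. For dose 3 v dose 1, add a between-arm WMW test on each subject's change against Arm 4c, keeping Arms 2c and 2d separate because their third doses differ.

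At dose 4, report the arm comparison without using change from dose 1 as the reference. State that the control vaccine becomes Menactra and that the dose is open-label. In the predecessor, local reactions in controls fell from 30% after dose 1 to 15% after Menactra, while vaccinees stayed at 42% and 43%. A change contrast there would show a relative increase arising largely in the control arm, where the vaccine had changed.

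The data are already collected, so the work is a change of SAP wording. The real cost is timing. Section 3.5.2.2 shows that doses 1 to 3 have been unblinded and reviewed for safety, so the new tests must be labelled post hoc for those doses. Three endpoints by two arms also make six tests, which should be read as exploratory.
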